Statistical Analysis Plan

Full Title of Study	Anti-Stress Intervention Among Physicians Study (ASIP)
Short-Title	ASIP study
Principal Investigator	[name] Institute of Public Health, Charité – Universitätsmedizin Berlin, corporate member of Freie Universität Berlin and Humboldt-Universität zu Berlin, Berlin, Germany
Protocol Identification Number	-
ClinicalTrials.gov identifier	NCT06368791
Author	Responsible statistician: [name] Digital Health – Machine Learning Group, Hasso Plattner, Institute for Digital Engineering, Potsdam, Germany & Hasso Plattner Institute for Digital Health at Mount Sinai, Icahn School of Medicine at Mount Sinai, New York, NY 10029, USA & Department of Statistics, Harvard University, [name], USA Responsible PI: [name] Institute of Public Health, Charité – Universitätsmedizin Berlin, corporate member of Freie Universität Berlin and Humboldt-Universität zu Berlin, Berlin, Germany
Version	01
Document Date	August 24, 2024
Sponsor	Charité University, Berlin, Germany

Inhaltsverzeichnis

Introduction	3
Study Methods	3
Statistical Analysis	3
Trial Profile	3
Baseline Characteristics of Participants.....	3
Analysis Principles for Final Analyses	3
Analyses of Individual N-of-1 Trials	4
Analyses of the Aggregated N-of-1 Trials.....	4
Effect Measure Modifiers	5
Additional Analyses	5
Protocol deviations.....	5
Missing Data	5
Analysis Populations: Intention-To-Treat (ITT).....	5
Safety and Adverse Events	6
Statistical Software	6
Difference to trial protocol.....	6
References.....	7

Introduction

Please see the study protocol paper for more information:

<https://www.frontiersin.org/journals/psychiatry/articles/10.3389/fpsy.2024.1420097/full>

Study Methods

Please see the study protocol paper for information on the study methods:

<https://www.frontiersin.org/journals/psychiatry/articles/10.3389/fpsy.2024.1420097/full>

Statistical Analysis

Trial Profile

A CENT CONSORT extension (1) flow chart will be used to show the flow of participants through the study.

Baseline Characteristics of Participants

The initial participant characteristics will cover both demographic and work-related aspects. Categorical data will be represented by their counts and relative percentages. For continuous data, the summary will include the mean, standard deviation, range (minimum and maximum), or median along with percentiles.

Analysis Principles for Final Analyses

The primary analyses will provide individual-level and population-level estimates of the average efficacy of anti-stress interventions in reducing same-day stress levels and reducing the level of expected stress on the following day (the two primary outcomes) based on the series of N-of-1 trials. Both individual-level and population-level analyses will be based on the intention-to-treat population. That is, the individual-level analyses will include all observed data points and the pre-specified intervention schedule, independently of whether the intervention was performed. The population-level analyses will include all participants of the study population that started a trial and their pre-specified study design and intervention schedule, and all their recorded data, independently of whether the intervention was performed as pre-specified and independently if or when the study participants dropped out of the study. As a result of this, all analyses will evaluate the effect of the availability of the anti-stress interventions which mirrors the effect of the intervention if there is high adherence to the pre-defined intervention schedule.

Analyses of Individual N-of-1 Trials

At the end of the individual N-of-1 trials, statistical analyses will be conducted to compare the outcomes of anti-stress interventions vs. no treatment. In a first step, the data will be presented descriptively by producing line plots of the N-of-1 trials. In a second step, Bayesian linear regression models with normally distributed errors will be used to compare the average ratings of same-day stress levels and the level of stress expected for the following day (the two primary outcomes) during periods of anti-stress interventions to those with no treatment using R's "brms" package. Non-informative priors will be used for all parameters since no prior information was available before the study to provide a reasonable effect estimate of anti-stress interventions in reducing daily stress levels. Given the longitudinal nature of our data, we will employ a first-order autoregressive (AR1) error structure to recognize that measurements taken at adjacent times have a higher dependence compared to those taken at more distant intervals. Algorithm convergence will be assessed by the parameters R^2 , Bulk_ESS and Tail_ESS and assumptions of the models will be checked. Separate analyses will be performed for each individual to compare the average response to treatment. Based on this model, estimates of the posterior distribution of the average anti-stress intervention effect on the primary outcomes (daily stress and expected level of stress for the following day) at the individual level will be obtained. We will report the mean posterior distribution and the 95% credible interval. Additionally, we will report the probability to achieve a clinically relevant intervention effect which is defined as a reduction of 0.5 points of the stress scale (range 1 to 10).

Analyses of the Aggregated N-of-1 Trials

In order to estimate population-level intervention effects, a Bayesian multi-level linear regression model will be utilized to evaluate the efficacy of anti-stress interventions compared to no treatment on the primary outcomes, the same-day stress levels and the level of stress expected for the following day, at the population level. This will be done separately for those participants that chose the mindfulness intervention and the box breathing exercise. Bayesian multi-level mixed models will be employed to estimate the posterior distribution of the population-level average treatment effect. For the aggregated analysis, non-informative priors will be used for all parameters since no prior information was available to reasonably estimate the effect of anti-stress interventions on reducing daily stress levels. In line with the analyses of the individual N-of-1 trials described above, we will include a first-order autoregressive (AR1) error structure to account for the higher dependence of measurements taken at adjacent times compared to those taken further apart. Similar to the individual-level model previously described, estimates of the posterior distribution of the average anti-stress intervention effect on the population level in reducing daily stress levels will be obtained. The posterior distribution of the mean difference between the outcomes of anti-stress interventions and no treatment will be derived from the aggregated Bayesian model. Similarly to the individual-level analyses, we will report the mean of the posterior probability distribution, the 95% credible interval, and the probability to achieve a clinically relevant reduction in stress levels of 0.5 points.

As a secondary analysis, we will perform a joint analysis of both interventions to estimate the effect of the availability of an anti-stress intervention among the participants who

chose the respective intervention on the daily stress level and the level of stress expected for the following day. Secondary outcomes will be modeled and reported similarly.

Effect Measure Modifiers

The impact of baseline effect measure modifiers, which were recorded before randomization to the treatment schedule, namely sex, the baseline stress level (Cohen's PSS) and the place of work (hospital vs. outpatient clinic), will be assessed exploratively in stratified subgroup analyses and by incorporating these variables as interaction terms in the Bayesian models.

Additional Analyses

As additional analyses, frequentist linear mixed regression models are calculated using the same model-specifications as described for the Bayesian models above. Additionally, a per-protocol analysis will be performed (see below).

Protocol deviations

Protocol adherence will be assessed by comparing the response to the daily question about the performance of the intervention/exercise matches with the current period (intervention vs. control). Additionally, if less than $n=16$ PROs are documented, the participant will be excluded from the per-protocol analysis which will be performed as part of the sensitivity analyses.

Missing Data

Regarding the data obtained from the StudyU App, we will conduct complete-case analyses, assuming that the missing values are completely random. If participants did not complete the N-of-1 trial, we will analyze all the available data. In the psychological questionnaires, the final scores are calculated as the mean of all answered items. If more than 50% of the items remain unanswered, a score is not calculated.

Analysis Populations

Intention-To-Treat (ITT)

The main analyses utilize the ITT population, which includes all randomized participants, irrespective of whether they completed the entire study period and received the assigned intervention. Data from participants who did not complete the N-of-1 trial will be included in the analyses up to that point.

Per-Protocol (PP)

As an additional analysis, a per-protocol analysis will be performed including only participants with at least $n=16$ documented PROs and a protocol adherence of 85% or higher.

Safety and Adverse Events

Adverse events were not recorded during the study period but are assessed as part of the follow-up questionnaire and will be reported descriptively.

Statistical Software

Analyses will be conducted using R version 4.4.1.

Difference to trial protocol

--

References

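### The primary models name no day or period term, so drift aligned with a participant's treatment sequence enters that individual's effect estimate

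*SAP*

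**What the plan says.** Under Analyses of Individual N-of-1 Trials, the SAP fits a Bayesian linear regression with normal errors to each participant, to "compare the average ratings of same-day stress levels and the level of stress expected for the following day" under the two conditions. Its one time-related element is stated there: "we will employ a first-order autoregressive (AR1) error structure to recognize that measurements taken at adjacent times have a higher dependence".

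Under Analyses of the Aggregated N-of-1 Trials, the multilevel model repeats this ("we will include a first-order autoregressive (AR1) error structure to account for the higher dependence of measurements taken at adjacent times"), and "The posterior distribution of the mean difference between the outcomes of anti-stress interventions and no treatment will be derived from the aggregated Bayesian model".

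Neither section names a day, period or cycle term. The only covariates named are sex, baseline perceived stress and place of work, as exploratory effect modifiers that were "recorded before randomization to the treatment schedule". The frequentist models under Additional Analyses share the Bayesian specification. Line plots and a check of model assumptions are planned, but nothing is said about what follows if a trend is seen. For non-completers, the ITT section says: "Data from participants who did not complete the N-of-1 trial will be included in the analyses up to that point".

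Individual-level estimates are among the primary results (Analysis Principles for Final Analyses). Each is reported with the probability of a reduction of at least 0.5 points on the 1-to-10 scale.

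**The concern.** AR(1) errors describe how residuals on neighbouring days resemble each other around a constant mean within each condition. A gradual rise or fall in stress over the trial is a change in the mean, which this structure does not take out. Settling after enrolment, shifting workload or habituation to daily self-rating could each produce one.

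If intervention days fall on average earlier or later than control days, part of the drift is attributed to the intervention. The schedule is randomised, so two participants with the same true response and the same drift could get different estimates and different probabilities of a relevant reduction purely because of the order drawn. Early stopping can unbalance a sequence that was symmetric when assigned. For an individual result, which the SAP treats as primary, this error is not averaged away.

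**Working it through.** The SAP states no figure that can be reproduced here. The 0.5-point threshold is the SAP's. All else is assumed: 28 days, residual SD 1.5, AR(1) parameter rho from 0 to 0.6, a linear fall of 1 point from first to last day, and no true effect. A is intervention and B is no treatment. The effect is A minus B, so a negative value looks like benefit.

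**Bias with independent errors (rho = 0).** Bias = (mean day of B − mean day of A) × drift per day, with drift per day 1/27.
- ABAB, 7-day periods: mean day of A = (4 + 18)/2 = 11; of B = (11 + 25)/2 = 18; bias 7/27 = +0.26. BABA gives −0.26.
- AB, 14-day periods: (21.5 − 7.5)/27 = 14/27 = +0.52. BA gives −0.52.
- ABBA complete: both mean days are 14.5; bias 0.
- ABBA stopped after three periods: (14.5 − 4)/27 = +0.39. After two: 7/27 = +0.26.

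**Bias with AR(1) errors.** Generalised least squares (GLS), equivalent to a flat prior with known rho:

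| Sequence | rho 0 | rho 0.3 | rho 0.6 | SE ratio with day term (rho 0 / 0.3 / 0.6) |
|---|---|---|---|---|
| ABAB, 7-day | 0.26 | 0.23 | 0.14 | 1.11 / 1.10 / 1.06 |
| AB, 14-day | 0.52 | 0.49 | 0.39 | 2.00 / 1.81 / 1.45 |
| ABBA, 7-day, complete | 0 | 0 | 0 | 1.00 / 1.00 / 1.00 |
| ABBA, 7-day, stopped after three periods | 0.39 | 0.36 | 0.27 | – |

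The sign reverses for the opposite order, and the bias scales with the drift. At rho 0.9 it falls to about 0.03 (ABAB) and 0.11 (AB). A linear day term brings it to 0 in every case.

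Simulation with rho estimated (REML, 400 runs per sequence, 2-point fall, rho 0.3) agrees: +0.45 and −0.38 for ABAB and BABA, +0.91 and −0.93 for AB and BA, +0.02 for ABBA. Estimating rho therefore does not absorb the drift.

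**Effect on the reported probability.** P = Φ((−0.5 − bias)/SE). For four 7-day periods at rho 0.3, SE = 0.679. With a 2-point fall, bias = ±0.453. At the expected estimate:
- no drift: Φ(−0.5/0.679) = 0.23
- BABA: Φ((−0.5 + 0.453)/0.679) = 0.47
- ABAB: Φ((−0.5 − 0.453)/0.679) = 0.08

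Averaging over sampling variation replaces SE by √2 × 0.679 = 0.960 and gives Φ(−0.521) = 0.30, Φ(−0.049) = 0.48 and Φ(−0.993) = 0.16. The gap narrows, but its direction stands.

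**Total error of an individual estimate (rho 0.3).** RMSE = √(SE² + bias²).
- ABAB, 1-point drift: √(0.679² + 0.227²) = 0.72 without the day term, 0.75 with it.
- ABAB, 2-point drift: √(0.679² + 0.453²) = 0.82 without, 0.75 with.
- AB, 1-point drift: √(0.731² + 0.494²) = 0.88 without, 1.33 with.

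**Population level.** Assume 50 participants on ABAB or BABA, rho 0.3, a common 1-point drift, participant intercepts and a common effect. SE = 0.679/√50 = 0.0961.
- Split 25:25: bias 0; SE 0.0961 with or without a common day slope. Individual biases of ±0.227 still add an SD of 0.227 to the apparent between-person variation in effect.
- Split 30:20: bias = (30 − 20)/50 × 0.227 = 0.045. A common day slope removes it, with SE 0.0964.

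**The case against.** The strongest reply is that the simpler individual model is a defensible bias–variance choice. That stands. For alternating 7-day periods and a 1-point drift, the unadjusted estimate has slightly smaller total error, and its 95% interval still covers about 93.7%. With one switch, adjustment is clearly worse on total error at that drift, although simulated coverage without the term was about 87%. Nothing in the SAP points to a single-switch design.

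A reader might infer more than the SAP supports:
- That all drift is counted as intervention effect. Only the part aligned with the sequence enters, and that can be zero.
- That the population effect is biased. Under balanced mirror-image sequences a common drift cancels in expectation, and the SAP shows no imbalance.
- That no planned analysis could reveal drift. The line plots and assumption checks might. The gap is that no action is tied to them.
- That the SAP rules out a time term. It gives no model equation and is silent, which leaves the choice open until the data are seen.
- That participants would be given misleading results. The SAP says individual results will be reported, not that they are returned to participants.

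The sequence set and trial length belong to the protocol paper, which the SAP cites for study methods, so their absence is not a fault here. Model specification is the SAP's own task.

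**Conclusion.** The point holds at individual level. Without a day or period term, drift aligned with the sequence enters the individual effect and its probability, with the sign set by order. The share is about a quarter of a linear drift for alternating 7-day periods, about half for one switch, none for a completed symmetric sequence, and about 0.36 of it for a symmetric sequence cut after three of four periods. These shares rest on 28 days and rho 0.3, and they shrink as rho rises. The probabilities also rest on SD 1.5. Under these assumptions a 2-point drift shifts an alternating-sequence estimate by about 0.45, close to the SAP's 0.5-point threshold. The SAP gives no evidence on how large drift is, so the actual bias is unknown and may be nil.

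At population level the consequence is mainly inflated between-person variation in effect, plus a small bias if sequences or dropouts are unbalanced. This is an inexpensive improvement to the specification. It does not show that the primary model is invalid.

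**What to change.** - **Multilevel model:** add a centred population day slope and, where estimable, a participant-varying day slope. Under the assumptions above, the common slope costs almost no precision (SE 0.0961 to 0.0964 at a 30:20 split).
- **Individual models:** keep the present primary model. Pre-specify a sensitivity fit with a centred day term, and report its effect and probability of a 0.5-point reduction beside each primary result.
- **Frequentist models:** carry the same terms over.
- **Line plots and assumption checks:** state that a visible trend directs the reader to the adjusted estimate, so that the choice of primary model is not made after seeing the data.

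The change needs SAP wording and extra model runs, but no new data. The adjusted individual intervals are wider. For rho 0 to 0.6, SE rises about 6–11% for four alternating 7-day periods, 0% for a completed symmetric sequence and about 45–100% with one switch. In that last case day and condition are close to collinear, so both estimates should be read together. A linear term removes only linear drift.

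### Does the unstated time index let the AR(1) error treat ratings on either side of unlogged days as consecutive?

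*SAP*

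**What the plan says.** In *Analyses of Individual N-of-1 Trials*, the Bayesian regression for each participant carries serially correlated errors: "we will employ a first-order autoregressive (AR1) error structure to recognize that measurements taken at adjacent times have a higher dependence". The contrast it draws is with ratings further away in time. *Analyses of the Aggregated N-of-1 Trials* repeats the choice for the multi-level model: "we will include a first-order autoregressive (AR1) error structure to account for the higher dependence of measurements taken at adjacent times". *Additional Analyses* passes it on: "frequentist linear mixed regression models are calculated using the same model-specifications".

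Under *Missing Data*, the rule for the app ratings is "we will conduct complete-case analyses, assuming that the missing values are completely random". *Analysis Principles for Final Analyses* sets no minimum for the main analysis: "the individual-level analyses will include all observed data points and the pre-specified intervention schedule". *Analysis Populations* says of early leavers: "Data from participants who did not complete the N-of-1 trial will be included in the analyses up to that point". The only floor, under *Protocol deviations*, concerns a sensitivity analysis: "if less than $n=16$ PROs are documented, the participant will be excluded from the per-protocol analysis".

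No section names the time variable of the AR(1) term or says how an internal gap is handled.

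**The concern.** An AR(1) error needs an index. With a rating every day, row number and study day coincide and nothing hangs on the choice. Once days are missing and their rows removed, the two differ. On row order, the last rating before a gap and the first after it are treated as neighbours, which is the opposite of the reason the SAP gives for using AR(1).

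The stakes would be the calibration of the 95% credible intervals and of the reported probability of a 0.5-point reduction. With multi-day treatment periods, a gap at or near a switch makes the before-and-after comparison look more precise than it is. This can happen even if missingness is unrelated to stress. The aggregated and frequentist models would inherit the choice. Two analysts could follow the same text and fit different covariance structures, so it looks like something the plan should pin down.

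**Working it through.** **1. What the text supports.** The individual section contrasts adjacent times with "compared to those taken at more distant intervals", and the aggregated section draws the same contrast. Both describe dependence that fades with time, and only a study-day index delivers that across a gap. The complete-case rule decides which values enter the likelihood. It does not say how the remaining values are spaced. The passages do not conflict. What is missing is a line of model code.

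**2. What the index changes.** For ratings d days apart with no logged rating between them, and daily coefficient ρ:

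- study-day index: correlation = ρ^d
- row index: correlation = ρ

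Across seven unlogged days, d = 8. At ρ = 0.7 the study-day value is 0.7^8 = 0.058, and the row value is 0.7. For a given coefficient, both fits give a generalised-least-squares contrast, so under completely random missingness neither biases the effect. Only precision and its reporting differ.

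**3. Size at the individual level.** The SAP states no trial length, period length, autocorrelation or missingness rate, so there is no figure of its own to reproduce, and every design below is assumed. Series were simulated with a true effect of −0.5, days were deleted, and the same data were fitted with both indices under flat priors. The design was 28 days in four 7-day periods, error SD 1.5, 4000 runs, with paired Monte Carlo error of at most 0.4 point. Coverage of the 95% interval (%):

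| Pattern | ρ | Row | Day | Loss |
|---|---|---|---|---|
| 15% at random | 0.4 | 94.5 | 94.9 | 0.4 |
| 30% at random | 0.4 | 93.5 | 94.1 | 0.6 |
| 16 of 28 entries | 0.4 | 93.3 | 94.3 | 1.0 |
| 7-day gap plus 10% | 0.4 | 92.7 | 93.7 | 1.0 |
| 15% at random | 0.7 | 92.7 | 93.5 | 0.8 |
| 30% at random | 0.7 | 91.3 | 93.0 | 1.7 |
| 16 of 28 entries | 0.7 | 90.7 | 92.8 | 2.1 |
| 7-day gap plus 10% | 0.7 | 88.8 | 92.3 | 3.5 |

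A separate run of 1500 replicates gave losses of 0.3 and 0.8 at ρ = 0.4 (15% and 30% missing), 1.0 and 1.8 at ρ = 0.7, and 4.3 (88.8 against 93.1) for ρ = 0.7 with a week-long gap.

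A third run (28 or 56 days, 7-day periods, ρ of 0.3, 0.6 and 0.8, 1000 replicates) gave losses of 0 to about 2 points at 20% random missingness, 0 to about 4 at 43%, and about 1 to 8 with 4-day runs. It was about 3 to 12 points when the last two days of every period were missing (worst case 79.7 against 91.6, 28 days, ρ = 0.8).

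**4. How much belongs to the index.** With 16 of 28 entries and ρ = 0.7, the shortfall from 95 is 95 − 90.7 = 4.3 points by row and 95 − 92.8 = 2.2 by day, so about half remains with the day index. The mean AR estimate is 0.46 by row and 0.49 by day, against a true 0.7. Of the bias of 0.24, 0.21 is there either way. When the true reduction is exactly 0.5, a probability of at least 95% is reported in 7.8% of runs by row and 6.7% by day (nominal 5%). With no missing days at ρ = 0.8, both fits cover 92.2%. Short series explain much of what looks like an indexing fault.

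**5. Where it vanishes or turns round.** Dropout after day 16 gives 92.4 with either index, because it leaves no internal gap. With daily alternation, ρ = 0.7 and a 7-day gap, row order over-covers (97.4 against 96.4).

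**6. Population level.** With 30 participants, ρ = 0.7, a random intercept only and a common effect, coverage is 90.8 against 93.6 (30% missing) and 87.4 against 94.0 (7-day gap). With random slopes (SD 0.5), row-order intervals are not narrower (standard-error ratio 1.00 to 1.06), and the estimate is about 1 to 9% more variable. The SAP does not fix the random-effects structure, so no population-level loss can be attributed to it.

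**The case for a change.** The strongest case for a change is that the error structure and the missing-data rule both sit in the SAP, and together they leave the covariance undefined whenever a series has an internal gap. Intent does not write code, and a one-sentence statement would cost nothing. Gaps that cluster without regard to stress values still satisfy the plan's missingness assumption, and those are where row order does worst. Days missed regularly at the end of each period could cost many points even at moderate autocorrelation (84.9 against 93.0 at ρ = 0.6 over 28 days).

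Part of this stands. The index is unstated, the row-order fit is inferior when gaps exist, and clustered gaps make it clearly so. But the harm needs a coding choice that the SAP does not make and that runs against its stated reason for the AR(1), together with substantial autocorrelation and an unfavourable gap pattern. The document supplies none of these. Nor does the 16-entry floor show that internal gaps are common. Without a trial length it cannot be read as a share of days, and it may equally be aimed at early dropout, which is harmless here.

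**Conclusion.** This is a gap in detail that an analyst following the SAP's own rationale fills sensibly, and the plan need not change. The text points to study-day spacing, and on that reading the model is sound. If row order were used despite that, individual intervals under multi-day periods would lose about 0 to 2 coverage points with scattered gaps of 15 to 30%, and about 1 to 4 points with a week-long gap, in assumed 28-day designs with ρ of 0.4 to 0.7. Larger losses need gaps that recur at period switches. The direction reverses under daily alternation, terminal dropout is unaffected, and a good part of the shortfall from 95% remains with the correct index. The effect estimate is not biased under the plan's missingness assumption. The simulations approximate the planned models, because the SAP gives no model code. The conclusion would change only if the analysis code turned out to run the AR(1) on row order in data with long or systematic gaps.

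### Do separate individual fits need a minimum number of observed days in each condition before an effect is reported?

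*SAP*

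**What the plan says.** Under Analysis Principles for Final Analyses, the SAP gives individual results primary status: "The primary analyses will provide individual-level and population-level estimates of the average efficacy of anti-stress interventions". The same section fixes the data they use: "the individual-level analyses will include all observed data points and the pre-specified intervention schedule".

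Under Analyses of Individual N-of-1 Trials, each participant gets a separate Bayesian regression with AR(1) errors ("Separate analyses will be performed for each individual to compare the average response to treatment"). On priors it says: "Non-informative priors will be used for all parameters since no prior information was available before the study to provide a reasonable effect estimate". A line plot comes first. The report then gives a posterior mean, a 95% credible interval and the probability of a reduction of 0.5 points on the 1-10 scale. Convergence statistics are examined, among them "Bulk_ESS and Tail_ESS and assumptions of the models will be checked".

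On early stoppers, the ITT paragraph under Analysis Populations says: "Data from participants who did not complete the N-of-1 trial will be included in the analyses up to that point". The only rule on data quantity belongs to the per-protocol set, "including only participants with at least $n=16$ documented PROs and a protocol adherence of 85% or higher", and it counts ratings in total. The multi-level model is described for the group result only: "Bayesian multi-level mixed models will be employed to estimate the posterior distribution of the population-level average treatment effect".

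**The concern.** Read together, these rules ask for an individual effect and a 0.5-point probability for every randomized participant, however little was recorded. Someone who stops during the first period has ratings under one condition only. The model then has two mean parameters (intercept and treatment effect) and information on only one of them.

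The reported probability would then describe the prior and not the person. A value near one half could be read as an even chance of benefit. The convergence check need not catch this, because a sampler drawing from a proper prior converges perfectly well. The 16-rating rule does not help either: it does not apply to the ITT analysis, and 16 ratings under one condition would satisfy the count. Since the individual effects are primary results, a minimum number of days per condition, pooled individual estimates and named priors all look like natural additions.

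**Working it through.** The SAP states no sample size, power or precision for the individual fits, so there is no figure to reproduce. The residual SD, period length, dropout rate and prior scale are not in the SAP; the values below are assumptions.

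**1. One condition only.** The design matrix [1, x] with x constant has rank 1 for 2 coefficients, and AR(1) errors do not change that. Under a flat prior the posterior of the effect is improper. Under an independent normal(0, s) prior the posterior of the effect equals the prior, so P(reduction of at least 0.5) = Φ(−0.5/s) and the 95% half-width is 1.96·s:

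| s | Φ(−0.5/s) | Half-width |
|---|---|---|
| 2.5 | Φ(−0.20) = 0.42 | 4.9 |
| 10 | Φ(−0.05) = 0.48 | 19.6 |
| 100 | Φ(−0.005) = 0.50 | 196 |

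A four-chain sampler on seven control-only days gave R-hat 1.00, full effective sample size, and probabilities of 0.41, 0.48 and 0.50 for the same three priors. The convergence check is indeed silent with a proper prior. The interval is not silent: even at s = 2.5 it is 2 × 4.9 = 9.8 points wide, on a scale that spans 10 − 1 = 9.

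**2. Few days in one condition.** With a flat prior and independent errors, the half-width is t(0.975, n1+n2−2) · SD · √(1/n1 + 1/n2). For SD 1 to 2:

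| Days | Factor at SD 1 | Half-width, SD 1 to 2 |
|---|---|---|
| 7 and 1 | 2.447 × 1.069 | 2.6 to 5.2 |
| 7 and 2 | 2.365 × 0.802 | 1.9 to 3.8 |
| 15 and 1 | 2.145 × 1.033 | 2.2 to 4.4 |
| 5 and 5 | 2.306 × 0.632 | 1.5 to 2.9 |

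The effect is defined in every row, and the interval states how little is known. A minimum of five days per condition would still leave an interval of about three to six times the 0.5-point threshold (1.5/0.5 = 3; 2.9/0.5 = 5.8).

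**3. How many participants.** If a share h drops out per day and the first period lasts L days, the one-condition share is 1 − (1 − h)^L. For h = 0.005, L = 2: 1 − 0.995² = 1%. For h = 0.03, L = 14: 1 − 0.97¹⁴ = 35%. For L = 7 the range is 3% to 19%. Both inputs are assumed, so the SAP supports no particular value.

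**4. Would pooling help?** Assume 28 days in 7-day blocks, AR 0.3 and SD 1.5; the standard error of one person's effect is then 0.68. With a known between-person SD τ, the ratio of pooled to standalone root mean squared error is √(τ²/(τ² + 0.68²)). This is 0.76 at τ = 0.8 and 0.59 at τ = 0.5, a reduction of 24% to 41%.

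Classification around the 0.5-point threshold is less favourable. At SE 0.70 and τ = 0.5, misclassification standalone against pooled is 24% against 15% at a group mean of 0, 30% against 30% at −0.5, and 28% against 23% at −0.8. The gain at 0 arises because pooling labels nearly everyone a non-responder: it misses 84% of true responders, against 36% standalone. At a group mean of −0.8 the harm reverses. For people whose true effect is zero (SE 0.57 to 1.24, τ 0.3 to 0.5), 42% to 100% have a pooled estimate beyond −0.5, against 19% to 34% standalone.

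**The case for a change.** The strongest case for a change is that the defect follows from the SAP's own rules and needs no assumed SD or schedule. The SAP foresees dropout, requires a primary quantity for each person, and sets a data minimum for the per-protocol set but none here. A flat-prior fit might fail the convergence check, but no action on failure is written down, so the handling would be settled after the data are seen. A sentence or two would close the gap.

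The non-identifiability stands, and so does the silence of the convergence check under a proper prior. What does not stand is that this would mislead or leave a consequential choice open. The probability is never reported alone: a mean near zero, an interval about as wide as the scale or wider, and a plot showing one condition come with it. The only sensible handling is to call the effect not estimable, and choosing this after seeing which condition is missing cannot favour either result.

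The wider remedies are weaker still. A five-day minimum is arbitrary and cuts against the stated principle of using all observed data. Pooling answers a different question from a standalone N-of-1 effect, has the costs shown above, and still gives a one-condition participant no contrast of their own. Naming the priors would add detail but would not identify the effect.

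**Conclusion.** The observation is correct and narrow: a participant rated under one condition only has no individual effect that the data can identify, and the SAP does not say what is then reported. No change is needed. It is a gap that analysts fill sensibly by listing the effect as not estimable, showing the line plot and keeping the person in the multi-level model. With one or two days in a condition, the wide interval is the right answer and not a fault.

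The identifiability result rests on algebra alone. The prior-only figures (0.42 to 0.50, with ±4.9 or wider) assume a normal prior for the effect with SD 2.5 to 100. The number of participants affected is unknown, because period length and dropout are not in the SAP, which refers to the protocol paper for study methods. Population-level estimates are not touched. A five-day minimum, pooled individual effects and named priors remain matters of preference.
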